## **8. PROTECTION OF HUMAN SUBJECTS**

### **8.1. Ethical approval and subject consent**

This observational study will be performed in accordance with ethical principles that are consistent with the Declaration of Helsinki, Good Participatory Practice (GPP) and the applicable legislation on Non-Interventional Studies and/or Observational Studies.

Ethical approval for the study will be sought from the appropriate REBs for the study, which is anticipated to include both Institutional Review Boards (IRBs) and an

Independent Ethics Committee (IEC), as appropriate for each included clinical site. The REBs must also approve any amendment to the protocol, according to local regulations.

### *User Survey*

Prior to completing the survey, all potential participants will be able to read the informed consent information, either electronically or as a paper version (if they select to complete a paper survey at a participating study site (to be confirmed). Consent will be indicated through the selection of a consent statement, and the provision of the participant's name, signature (electronic or wet ink, as appropriate), and the date of consent.

### *Apretude Supports Program Analysis (Secondary objectives)*

Participants in the Apretude Support PSP will have previously provided informed consent during enrolment and this consent permits the use of the participants' data for further research activities. Thus, no additional consent will be required for the purposes of this study.

## **8.2. Subject Confidentiality**

All participants will be assigned a unique study identification (ID) in the study database, that will not be linked to personal identifiable information. GlaxoSmithKline (GSK) will not have access to patient identifiers.

## **9. LEGAL BASIS FOR PROCESSING INDIVIDUAL HUMAN DATA**

The authors confirm that study data is Individual Human Data (IHD) owned by GSK and that:

- The proposed use of the IHD is **Study Use\*** as outlined in the patient consent/consent waiver (HCP and User Surveys).
- The study IHD will be anonymized as described in VQD-STD-000324 (Apretude Supports Program Analysis).

\* Study Use means - the use of IHD is as stated in the original study protocol and/or aligned with the informed consent form to answer the study objectives and satisfy regulatory requirements and learn more about the product studied and the disease/condition studied. This includes bringing the product to market or maintaining market access which includes working with government agencies, insurers or health care payers and aiding GSK's understanding of clinical efficacy, safety, or effectiveness of the product.

## 10. MANAGEMENT AND REPORTING OF ADVERSE EVENTS/ADVERSE REACTIONS

This study has safety objectives. Safety collection and reporting will correspond to the following study type:

HCP and CAB-LA User Surveys
 
Study type 1: Primary data collection studies with or without sites/investigators with safety objectives (or systematic collection of adverse events) where there is consent and/or data collection direct from patients.
	
These studies can identify solicited and spontaneous events

Retrospective Cohort Analysis
 
Study type 5: Secondary data collection studies including unstructured data with human review with safety objectives. An example is human review of verbatim text in a medical record as part of a chart review study.
	
These studies can identify pre-specified safety events in aggregate at prespecified study milestones (e.g., interim analysis, study end) study end but cannot identify spontaneous events

### Collection of adverse events/reactions (Solicited Events)

HCP and CAB-LA User Surveys
 
Solicited Events are defined as adverse events related to the GSK/ViiV product under evaluation, identified and systematic collected in the study database.
 
The primary objectives of this study are to evaluate the effectiveness of the aRMMs for CAB-LA within Canada. For the primary objective, the study outcomes will be collected using closed ended questions only and are related to the aRMM effectiveness endpoints that will not be collected and reported as safety events.
 
The secondary objectives of the study include describing the users’ experience of CAB-LA, the utilization patterns, including adherence and persistence, and reasons for discontinuation, which may include adverse events. Certain responses to specific questions in the User survey, as defined in the Safety Management Plan, will be captured as solicited events and systematically collected and entered in the study database during the study. These events should be reported to the GSK Safety department (timing and contact information provided in the safety management plan). Solicited events must be collected in the study database and reported to GSK for entry into the GSK Safety database. For primary data collection studies, where there is direct collection of data from patients, these will be classified as solicited individual

---

#{vault:document\_date\_\_v}

Protocol for Non-Interventional Studies PASS Studies and Non-PASS Studies (4.0) March 2024

Template Doc ID: TMF-15706807

Parent Doc ID: VQD-SOP-066694

case safety reports (ICSRs). Valid ICSRs will be managed, classified, and submitted for onward reporting to regulators in line with the appropriate time frames as detailed in the Safety Management Plan.

These will also be summarised in interim, if applicable, and final study reports.

Adverse events related to CAB-LA that are not systematically collected will be reported as spontaneous events as described below (see reporting section below).

Due to the well characterised safety profile of CAB-LA under evaluation; only the safety events specified in the study objectives will be solicited and systematically collected during the study.

### **Retrospective Cohort Analysis**

For CAB-LA exposed patients, pre-defined safety events of interest (e.g, reasons for discontinuation, which may include adverse events), will be systematically recorded in aggregate. These will be summarised in final study reports. This analysis is based on secondary use of existing health data and as such Individual Case Safety Reporting (ICSRs) to regulatory agencies is not required. These events are not entered into the GSK Safety database but review of study reports from the QC'ed study database will be performed by Global Safety as appropriate.

## **Reporting of adverse events/reactions (Spontaneous Events)**

### **HCP and CAB-LA User Surveys**

**Spontaneous Events** are defined as:

- Those unsolicited adverse events observed related to the GSK/ViiV product under evaluation but exempted from collection, as justified in the protocol.
- Those adverse events observed related to any GSK/ViiV product not under evaluation in the study.
- Any Adverse Drug Reactions observed related to non-GSK/ViiV product(s), for which the ADRs should be reported to the appropriate marketing authorization application of the product(s) or Health Authority per local regulations. Spontaneous events may be collected in the study database. If events are not collected in the study database, they are still reported to GSK for entry in the GSK Safety database.

Adverse reactions related to the GSK/ViiV product under evaluation, which are not systematically collected/solicited under the study objectives or related to any other GSK/ViiV product will be classified as spontaneous reports and reported to the GSK Safety Department. This includes serious adverse events (SAEs), pregnancies, pregnancy outcomes and incidents (including device deficiencies or malfunctions if applicable).

Healthcare professionals and consumers will be informed of the possibility to report suspected adverse reactions to the marketing authorisation holder or to the concerned competent authority via the national spontaneous reporting system. Study staff will be trained on how to report suspected adverse reactions.

Valid ICSRs will be managed, classified, and submitted for onward reporting to regulators as spontaneous in line with the appropriate time frames.

Spontaneous reports may be linked to specific studies in the GSK Safety database. In the case where they are linked to the study, these reports can also be summarised in interim, if applicable, and final study reports.

ADRs will be reported as spontaneous cases. A Safety Management Plan (SMP) will be developed as per [VQD-WI-053775: Non-Interventional Study Safety Management Planning](#). Reporting timelines and safety contact details will also be provided in accompanying SMP.

### **Retrospective Cohort Analysis**

This analysis is based on data previously collected for other purposes e.g., routine healthcare encounters. As such, there is no requirement for the collection and reporting of Individual Case Safety Reports (ICSRs). Although the study is based on human review of unstructured data, the nature of the secondary data protocol driven data collection and analysis does not allow for reporting of serious and non-serious AEs, pregnancy exposures, or incidents related to any GSK/ViiV product during the conduct of this research. In addition, the minimum criteria of identifiable patient, reporter, exposure and event, needed to report individual case safety reports may not be present in the information reviewed within the context of the study. The data also may lack an identifiable patient and reporter and may be insufficient to establish attribution between a potential safety event and an individual patient using a GSK/ViiV product.

## **11. PLANS FOR DISSEMINATING AND COMMUNICATING STUDY RESULTS**

Final results from the primary objectives of this study will be prepared and shared with HC in May 2026. An interim analysis report with results from the secondary objectives of this study will also be prepared for internal dissemination between Q1/Q2 2026 and summarized in an abstract for submission to a scientific conference (to be determined).

#{vault:document\_date\_\_v}

Protocol for Non-Interventional Studies PASS Studies and Non-PASS Studies (4.0) March 2024

Template Doc ID: TMF-15706807

Parent Doc ID: VQD-SOP-066694

**CONFIDENTIAL**

[Ex. Protocol Final](#)

A final study report and slide deck will be prepared for internal dissemination of full study findings in November 2027. It is anticipated that an abstract will be prepared for submission to a scientific conference (to be determined). In addition, a manuscript will be prepared for submission to a peer-reviewed scientific journal.

Abstract timing in both instances will depend on conference abstract submission timelines. Manuscript preparation is anticipated to begin in quarter four (Q4) 2027.

## ANNEX 1 TABLES

Variable	Description
Patient ID	Anonymized unique program identification number
Enrolment Date	The date on which the patient was successfully enrolled in the PSP
Patient Status	Current status of patient (On drug, Suspended, Discharged)
Patient Status Date	The date the patient was moved into current status
Appointment Number	Sequential appointment number associated with the appointment
Initiation injection Dosing Schedule	Identifies whether the patient is receiving dosing schedule.
2 nd initiation injection Dosing Schedule	Identifies whether the patient is receiving dosing schedule.
Patient File Appointments	The date on which drug was dispensed and/or administered
Days Supplied	Days of supply for each dispense/administration
Oral Lead-in	Indicator if the patient initiated the optional a lead-in (i.e., flag and/or date)
Injection type	Description of the type of injection (initiation, subsequent, or re-initiation)
First Dose Date	The date on which the patient initiated their 1st dose of APRETUDE injection
Initial Injection Dose	Dosage as indicated in the initial physician order
Current Injection Dose	Dosage as indicated in the most recent physician order
Baseline Target Treatment Date	Most recently set target date. Modification could be due to planned/unplanned missed infusions
Current Target Treatment Date	Target treatment date for that appointment record
Confirmed Appointment Date	The date of appointment
Missed Appointment date	Date of missed appointment(s)
Cancelled/Rescheduled Appointment Date	Date of cancelled/rescheduled appointment(s)
Reason for Missed Injection	Reason provided for cancellation/rescheduling of appointment(s)
Planned/Unplanned Oral bridging	Was the cancellation planned or unplanned
Oral Bridging Agent	The type of oral bridging agent taken from the planned missed injection
Oral Bridging Dose	The dosage of oral bridging agent taken from the planned missed injection
Oral Bridging or Planned Leave Start Date	The date on which the patient initiated cabotegravir tablets or other oral PrEP due to a planned missed injection
Oral Bridging or Planned Leave End Date	The date on which the patient discontinued cabotegravir tablets or other oral PrEP due to planned missed injection
Returned Appointment Date or Target Treatment Date	The target date of administration of APRETUDE following a planned missed injection
Re-initiation appointment date	The date of next scheduled appointment after the missed injection/appointment
Status Date Discontinued	The date on which the patient was identified as discontinued or opted out of the APRETUDE SUPPORTS PROGRAM.
Status Reason Discontinued	Reason the patient stopped APRETUDE therapy or left the APRETUDE SUPPORTS PROGRAM.
Missed Injection Status	Description of the patient's status following missed injection (HCP contacted, Oral bridging initiated, oral bridging completed)
Incomplete Reason	Reason the patient did not receive injection. Accompanies an 'incomplete' Injection Status only

#{vault:document\_date\_\_v}

Protocol for Non-Interventional Studies PASS Studies and Non-PASS Studies (4.0) March 2024

Template Doc ID: TMF-15706807

Parent Doc ID: VQD-SOP-066694

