**Table 12. Outcome assessed for secondary objective #9**

Category	Sub-category	Details
Utilization patterns	• Use of oral lead-in	
 
▪ Frequency of use
 
▪ Duration of use
 

	• Use of oral bridging	
	• Adherence to CAB-LA	
 
▪ Measured as proportion of days covered (PDC)                             
 
○ Ratio of number of days the user is covered by the medication during a specific period to the total number of days within that period                                     
 
• Measured on user’s coverage (days supplied) with CAB-LA
 
 
 
 
 

Category	Sub-category	Details
		
 
Based on available follow-up time within the Apretude Supports Program database
 

	
 
Timing of injections (relative to labeled dosing schedule)
 
	
 
Early, on-time, late (with 7-day grace period)
 

	
 
Gaps in therapy
 
	
 
Missed injections (relative to labeled dosing schedule), reasons for missed injections
 
Missed injections being planned or unplanned
 
Use of oral bridging, planned or unplanned                             
 
Type and frequency of oral bridging agents used
 
Duration of oral bridging
 
 
 

	
 
Persistence on CAB-LA
 
	
 
Time to discontinuation
 
% of users who remain on drug, and are still at risk of HIV infection, at end of follow-up (will depend on data availability for at-risk status, either through PSP variables or through linkage with survey data)
 

	
 
Discontinuation
 
	
 
Rates of discontinuation
 
Reasons for discontinuation
 

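### Adherence (PDC) rests on days supplied, which the programme database records per dispensing or administration, so a dose dispensed but injected late or never may count as covered days

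*Protocol*

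**What the plan says.** Protocol section 7.3.2, Table 12 (secondary objective 9), defines PDC as "Ratio of number of days the user is covered by the medication during a specific period to the total number of days within that period". Coverage is measured on the user's "coverage (days supplied) with CAB-LA", and the window is "Based on available follow-up time within the Apretude Supports Program database".

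Annex 1 lists the database fields:

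- Days Supplied: "Days of supply for each dispense/administration".
- Patient File Appointments: "The date on which drug was dispensed and/or administered".
- Incomplete Reason: "Reason the patient did not receive injection". It accompanies an incomplete Injection Status only, but Injection Status is not itself listed in Table 11 or Annex 1.
- Confirmed, missed and cancelled or rescheduled appointment dates. The confirmed date is described only as the date of the appointment.

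Section 5.1 says that a healthcare provider gives CAB-LA by intramuscular injection every two months, after two initiation injections one month apart. Section 7.2 (Setting) says that programme services may include dispensing and delivery as well as help with administration. Table 12 also reports injection timing (early, on time or late, with a 7-day grace period, against the labelled schedule) and missed injections with reasons, as outcomes separate from PDC.

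**The concern.** Days supplied is a natural basis for PDC when the user holds and takes the drug. Here the drug must be injected by a provider, so a dispensed dose gives no coverage until it is given. The supply field does not separate the two events, and Table 12 does not say which one starts coverage or that an injection must be confirmed.

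Taken literally, a dose can earn its full interval from the day it was dispensed, even if the injection came late or never happened. Doses that are delayed or not given would then push PDC upward. Adherence is named in secondary objective 9, strict adherence to the dosing schedule is one of the four key risk messages, and the utilization results are planned for an interim report, an abstract and a manuscript.

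**Working it through.** **Plan's own figure.** There is none to reproduce: the protocol gives no expected PDC, PDC threshold or PDC-based sample size. Table 13 concerns the surveys only.

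**Inputs from the protocol.** Covered days divided by days in the window (Table 12); two injections one month apart, then every two months (section 5.1).

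**Assumptions not in the protocol.** A 365-day window; 30 days' supply for the first injection and 60 for each later one; target days 0, 30, 90, 150, 210, 270 and 330; each calendar day counted once; overlap not carried forward.

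**Formula.** PDC = distinct covered days / 365, computed once with coverage starting at injection and once with it starting at dispensing. With every dose on target, both give 365/365 = 100%.

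| Scenario | Days covered from injection | PDC from injection | PDC from dispensing | Excess (points) |
|---|---|---|---|---|
| A. One maintenance dose dispensed, never injected | 365 − 60 = 305 | 83.6% | 100% | 16.4 |
| B. Two such doses | 365 − 120 = 245 | 67.1% | 100% | 32.9 |
| C. One injection 7 / 14 / 30 days late, later ones on target | 358 / 351 / 335 | 98.1 / 96.2 / 91.8% | 100% | 1.9 / 3.8 / 8.2 |
| D. Each maintenance injection 7 / 14 / 30 days after previous coverage ends; dispensing on original schedule | 330 / 309 / 270 | 90.4 / 84.7 / 74.0% | 100% | 9.6 / 15.3 / 26.0 |
| E. As D, but each dose dispensed 7 / 14 / 30 days before its own injection | 330 / 309 / 270 | 90.4 / 84.7 / 74.0% | 92.3 / 88.5 / 75.3% | 1.9 / 3.8 / 1.4 |
| F. Records dated at injection, and only for doses given | – | – | same as from injection | 0 |

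Uncovered days in D, counted from injection: five gaps of 7 = 35; four gaps of 14 = 56; three gaps of 30 plus the last 5 days of the year = 95. Uncovered days in E, counted from dispensing: four gaps of 7 = 28; three of 14 = 42; three of 30 = 90. The excess in E is the difference: 7, 14 and 5 days, or 7/365 = 1.9, 14/365 = 3.8 and 5/365 = 1.4 points.

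The error is therefore large when a dispensed dose is never given, or when dispensing keeps to the schedule while injections slip. It is small when dispensing follows the injections.

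**The case against.** The strongest reply is that this is a derivation rule. Section 7.7 leaves the analysis to the statistical analysis plan and shell tables, and section 7.4 says that the variables depend on what the programme collects. The anchor date could properly be set there. Table 12 itself speaks of days on which the user is covered, which a sensible analyst would read as after injection. The extract also includes appointment dates and Incomplete Reason, which could identify doses not given. The protocol gives no frequency for dispensed but uninjected doses.

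Much of this stands, and it limits the point to something that may happen. It does not remove it. The protocol did not leave the measure open: it chose days supplied and listed the fields. If the extract merges the two events, a later rule may be unable to separate them. The listed fields help only in part, because the confirmed appointment date does not say that an injection was given, and Injection Status is not requested.

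Four stronger readings are tempting, and the document does not support them:

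- That the plan states such doses count as covered. It does not; Table 12 never names Patient File Appointments as the PDC date and is silent on the anchor.
- That late or missed injections are hidden. Table 12 reports injection timing and missed injections separately.
- That a dose with both a dispensing and an administration record would be counted twice and push the ratio above 1. PDC as defined is a share of days, so it cannot exceed 1.
- That injection timing would be judged against a target date the programme can reset. Table 12 sets timing against the labelled schedule.

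**Conclusion.** The point holds as a poorly fixed measure. PDC is based on days supplied, the supply field merges dispensing with administration, and no confirmed injection is required. Under the stated assumptions, one user's one-year PDC could be overstated by about 16 points for each maintenance dose dispensed but never injected. If dispensing moves with late injections the overstatement is about 1 to 4 points, and if records are dated at injection it is zero. Larger values for repeated late injections (scenario D) require dispensing to keep to the original schedule throughout.

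These are per-user figures. The effect on the cohort depends on how many users are affected, which the protocol does not say. Section 7.7.1.1 summarises continuous utilization outcomes by median and IQR, so a few affected users would move the median little. The scope is secondary objective 9, which is descriptive and not mandated by Health Canada. The primary knowledge, attitude and behaviour objectives and the sample size are unaffected.

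**What to change.** In Table 12:

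- Start PDC coverage on the date the injection was administered.
- Give zero covered days to dispense-only records and to records with an incomplete injection status.
- Count each calendar day at most once.
- Use the same administered date for the early/on-time/late outcome, keeping the labelled schedule as its reference.

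In the data request, ideally before the interim extract, ask the programme vendor for separate dispensing and administration dates and for Injection Status, and add these to Table 11 and Annex 1. Where no administration date is held, use the confirmed appointment date if the record has no Incomplete Reason. Report how many records lack a confirmed administration, so that readers can judge how far PDC rests on this fallback.

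The cost is a wording change, minor programming and some records with a missing administration date. Because these are data already collected for another purpose, the vendor may not hold separate dates; the fallback and the reported count are there for that case.

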## ANNEX 2 DATA COLLECTION TOOLS

### *HCP Survey*

GK\_240144 HIV  
Apretude\_Combined :

---

### *User Survey*

GK\_240144 HIV  
Apretude\_Combined :User
